7.1.8 Device Deficiency

A **Device Deficiency** is any inadequacy of a medical device with respect to its identity, quality, durability, reliability, safety and performance. Device deficiencies include malfunctions, use errors and inadequate labeling. A device deficiency does not need to be related to an adverse event.

7.2 Safety Data Reporting

7.2.1 *Safety Data Reporting Responsibilities*

The responsibilities for safety data reporting in this retrospective review are summarized below.

- **Investigator:** The Investigator is responsible for recording all previously identified and newly identified adverse events and device deficiencies on the CRFs. Investigators must record on the source document and eCRF their opinion concerning the AE severity, relationship of the AE to device, seriousness categorization per the event definitions, and whether any device effect is anticipated or unanticipated. The Investigator will follow all IRB/EC and institutional reporting requirements of AEs and SAEs, including for any new safety information or adverse events which may be identified retrospectively. Investigators are required to prepare and submit complete, accurate and timely reports on this clinical investigation to the Sponsor, IRB/EC and/or regulatory authorities, when necessary.
- **Contract Research Organization (CRO):** The CRO is responsible for source data review of AEs and device deficiencies. As needed for monitoring activities, the CRO is responsible for appropriate follow-up with the Investigator, Sponsor and independent Medical Monitor, as per the study's Medical Monitoring plan. The CRO is also responsible for data management of this retrospective review.
- **Medical Monitor:** Each AE will be assessed by an Independent Medical Monitor for severity, relatedness to the device, seriousness categorization per the event definitions, and whether any device effect is anticipated or unanticipated. A firewall will be established between the Sponsor and its CRO representatives, and the independent Medical Monitor to reduce bias in adjudication of AEs.
- **Sponsor:** The Sponsor will assess all adverse device effects determined to be related to Irrisept based on the independent adjudication of the Medical Monitor. The Sponsor will investigate any reported device deficiencies as part of the complaint handling process and to ensure the deficiency could not lead to an adverse event if the problem were to recur. The Sponsor is responsible for any required safety reporting to the FDA or other regulatory authorities, such as per 21 CFR 803 (Medical Device Reporting), as applicable.

7.2.2 *Specific Considerations for AE Reporting*

1. Abnormal Vital Signs and Laboratory Values

Per Protocol IRR-CT-901-2013-01, it is the Investigator's responsibility to review all vital sign findings or laboratory results for possible AEs. Medical and scientific judgment should be exercised in deciding whether an isolated vital sign or laboratory abnormality should be classified as an AE. A vital sign or laboratory result should be reported as an AE if it meets any of the following criteria:

- Results in a change in study product use (treatment interruption)
- Clinically significant in the Investigator's judgment

2. AEs Occurring Secondary to Other Events

Per Protocol IRR-CT-901-2013-01, AEs occurring secondary to other events (e.g., cascade of events or clinical sequelae) should be identified by their primary cause, with the exception of severe or serious secondary events. However, medically significant AEs occurring secondary to an initiating event that are separated in time should be recorded as independent events.

3. Persistent or Recurring AEs

Per Protocol IRR-CT-901-2013-01, a persistent AE extends continuously, without resolution, between patient evaluation time points. Such events should only be recorded once on an AE CRF.

A recurrent AE resolves between patient evaluation time points and subsequently recurs, and each recurrence should be recorded separately on an AE CRF.

4. Use of Diagnosis for AE Reporting

Whenever possible, diagnoses should be given when signs and symptoms are due to a common etiology. For example, cough, runny nose, sneezing, sore throat, and head congestion should be reported as “upper respiratory infection”.

5. Preexisting Medical Conditions

Per Protocol IRR-CT-901-2013-01, a preexisting medical condition is present at the screening visit for that study. Preexisting medical conditions should be recorded on the AE CRF.

6. Deaths

Per Protocol IRR-CT-901-2013-01, all deaths that occur during the study, regardless of relationship to the study device, must be recorded on the AE CRF. Death should be considered an outcome and not a distinct event. The event or condition that contributed to the fatal outcome should be recorded on the AE CRF. The term “sudden death” should only be used for the occurrence of an abrupt and unexpected death due to presumed cardiac causes, pulmonary embolus (air embolus or fat embolus), or catastrophic stroke, in a patient without preexisting cardiac disease or history of TIA or stroke, within one hour of onset of acute symptoms, or in the case of unwitnessed death, within 24 hours of when the patient was last seen alive and stable.

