7. STUDY DATA PARAMETERS

The study data parameters are limited to the preexisting safety data from the closed study. This retrospective review involves identification, verification and adjudication of all adverse events in the study for all enrolled subjects based on the source medical records. The adverse events will be summarized by group, type, severity and device-relatedness. In addition, as part of the safety data review of the closed study, any device deficiencies with Irrisept documented in the source records during the closed study when the study device was used will be identified, even if the deficiency was not associated with an adverse event. Any device deficiencies will be investigated to ensure the deficiency could not lead to an adverse event if the problem were to recur.

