Exposure to non-sterile or contaminated product	
Potential for infection
 
 Product is aseptically-filled and bottle and applicator surfaces are terminally sterilized. Sterilization, packaging and manufacturing process validations have been completed to ensure product integrity and sterility. Product contains CHG, which acts as a preservative to inhibit microbial growth in the solution, and the product has been tested to show preservative effectiveness. Bottle and applicator are sequentially double wrapped with CSR wrap serving as a microbial barrier. Product has been tested to show stability and sterility are maintained over the labeled shelf life. Surgical patients routinely receive antibiotics as part of the pre-op and post-op surgical care regimen since surgical site infection is a known complication of any surgery type. 	
 - ADE: Minor surgical site infection, wound infection or abscess, as manifested by symptoms such as erythema, edema, pus, fever, chills, pain - SADE: Severe infection that requires or prolongs hospitalization, or requires medical or surgical intervention to prevent permanent impairment

TABLE 1: POTENTIAL RISKS AND ANTICIPATED ADVERSE DEVICE EFFECTS FOR IRRISEPT		
Potential Risk	Risk Assessment and Risk Mitigations	Potential Anticipated Effects
Use of product for irrigation affects wound healing	
Potential for delay in wound healing
 
 Patient contact materials have passed biocompatibility testing per ISO standard 10993-1. Manufacturing process controls ensure product is not contaminated with any particulates from manufacturing. 	
 - ADE: Minor wound dehiscence, non-healing wound, granuloma or adhesion - SADE: Severe wound dehiscence or non-healing wound that requires or prolongs hospitalization, or requires medical or surgical intervention to prevent permanent impairment

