Ineffective use of product with inability to remove wound debris	
Potential for ineffective irrigation or incomplete irrigation
 
 Surgeon routinely visually assesses surgical wound bed for effective debridement and clearance of particulates and wound debris. Saline is routinely available for surgical irrigation in the event that the Irrisept bottle cannot be used. 	
 - ADE: Minor non-healing wound, granuloma, adhesion, adverse tissue reaction or infection - SADE: Severe non-healing wound, granuloma, adhesion, adverse tissue reaction or infection that requires or prolongs hospitalization, or requires medical or surgical intervention to prevent permanent impairment
Incompatibility with other therapies used during the procedure	
Potential for incompatibility with other therapies (e.g., concomitant medications, other therapies used during surgery)
 
 No known incompatible medications or therapies with Irrisept. Irrisept is used an irrigation solution with short term exposure to the wound and surrounding tissues and is not ingested or injected. 	
 - ADE: Minor adverse tissue reaction - SADE: Severe adverse tissue reaction that requires or prolongs hospitalization, or requires medical or surgical intervention to prevent permanent impairment

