7.2.4 AE Severity

The AE severity will be determined by the Investigator and recorded on the AE eCRF. AE severity will be scored as follows:

GRADE	DESCRIPTION
0	No AE (or within normal limits)
1	Mild; asymptomatic or mild symptoms; clinical or diagnostic observations only; intervention not indicated
2	Moderate; minimal, local, or noninvasive intervention indicated; limiting age-appropriate instrumental activities of daily living (ADL)
3	Severe or medically significant but not immediately life-threatening; hospitalization or prolongation of hospitalization indicated; disabling; limiting self-care ADL
4	Life-threatening consequences; urgent intervention indicated
5	Death related to AE

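### The cascade rule in Protocol 7.2.2 lets minor wound events judged secondary go without their own AE record or adjudication, although Table 1 lists such event types as anticipated effects

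*Protocol*

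**What the plan says.** Protocol 7.2.2 item 2, carried over from the closed study's protocol, covers AEs that are secondary to another event, such as a cascade or sequela. They "should be identified by their primary cause, with the exception of severe or serious secondary events". The next sentence adds that "medically significant AEs occurring secondary to an initiating event that are separated in time should be recorded as independent events". Neither medical significance nor separation in time is defined. The first term appears elsewhere only in the Grade 3 description, "Severe or medically significant but not immediately life-threatening" (Protocol 7.2.4, repeated in SAP 3.8).

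Table 1 (Protocol 7.1.7, repeated in SAP 2.2.2) lists the non-serious effects anticipated with Irrisept. Under contamination it gives "ADE: Minor surgical site infection, wound infection or abscess", under wound healing "ADE: Minor wound dehiscence, non-healing wound, granuloma or adhesion", and under ineffective irrigation "ADE: Minor non-healing wound, granuloma, adhesion, adverse tissue reaction or infection".

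On scope, Protocol 7 states: "This retrospective review involves identification, verification and adjudication of all adverse events in the study for all enrolled subjects". Protocol 7.2.1 has the independent Medical Monitor assess every AE for severity, relatedness and seriousness, behind a firewall meant to reduce bias.

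The SAP does not restate the cascade rule and plans no output that would recover events reported under another event's term.

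**The concern.** Take a subject with an anastomotic leak and, close in time, a Grade 1 wound infection. If the site judges the infection to be a sequela of the leak, item 2 lets it enter the leak alone. The infection then has no term, grade or relatedness rating of its own, and the Medical Monitor has no separate event to rate.

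Calling an event secondary is a judgement about its cause. Here the site makes that judgement, and the site also documents which irrigation product was used (Protocol 9.1). The independent adjudication in 7.2.1 starts only once an AE record exists. For an irrigation device, minor infection and wound-healing events are among those the sponsor's own risk analysis anticipates, and the counts are meant to inform that risk assessment (Protocol 8.1, SAP 3.4).

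**Working it through.** No figure in the plan attaches to this rule, so the check is mainly a comparison of sections.

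**1. Which secondary events keep their own record.** The answer turns on the undefined term in the second exception.

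| Secondary event | Medically significant read as Grade 3 | Read as clinical judgement |
|---|---|---|
| Severe or serious | own record | own record |
| Grade 1-2, non-serious, close in time | folded | folded |
| Grade 1-2, non-serious, separated in time | folded | own record if the site thinks it significant |

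The middle row is folded on either reading. The last row depends on the reading, and on the second reading it depends on judgement at each of 17 sites.

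**2. Against the causality scale.** Protocol 7.2.3 rates an event Possibly Related when its timing fits device use, even though the subject's condition or another procedure could also explain it. A minor wound infection alongside a surgical complication can fit that category. Protocol 8.1 and SAP 3.4 count Possibly Related as potentially related. An event that the plan's scale could place in TAE04 may therefore never be put to the scale.

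**3. Whether another step restores the event.**
- Source review and full source data verification (Protocol 9.2) look for every potential AE, but recording follows a protocol that contains this rule.
- The AE form takes a description and the investigator's opinion on cause (Protocol 9.1). The folded event could be mentioned there, but it gets no coded term or rating.
- SAP 3.6 treats a missing relationship as potentially related. That default needs an AE record to act on.

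**4. Which outputs move.** A subject whose primary event is recorded still counts in the any-AE percentage. The loss falls on total events, preferred-term rows (TAE01, TAE05), TAE03a and possibly TAE04. ADE tables such as TADE01 move only if the event, once recorded, is rated as a device effect.

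**5. Scale.** Protocol 2.1 gives 600 subjects randomized 1:1. Group sizes by product actually used are not given, so equal groups are assumed: 600 / 2 = 300. One subject whose only event of a term is folded lowers that term's percentage by 1/300 = 0.0033, or 0.33 percentage points. Three such subjects in a group lower it by 3/300 = 1.0 point. The documents give no AE rate and no count of secondary events, so the number of such subjects is unknown.

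**The case against.** The rule is inherited on purpose. The review completes the closed study's safety endpoint with definitions consistent with that study (Protocol 6 and 7.1), and recording a cascade under its primary cause is a recognised choice. The second exception also deserves a fair reading. Severe events are already kept by the first sentence, so if medically significant meant only Grade 3, the second sentence would add almost nothing. The reading that gives it work keeps some non-severe events, and a wound infection appearing well after a leak is a plausible example. The Medical Monitoring Plan, which will describe the adjudication process, is not among the documents.

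These points limit the concern without removing it. Minor events close in time remain folded on any reading, and capture of the others is left to undefined terms. Inheritance is no bar, since Protocol 7.1 already adds clarifications to the closed study's definitions.

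A reader might go further in three ways that the documents do not support:
- **That the rule removes every minor wound event following a complication.** The trigger is being secondary to another event, not coming after it, and the second exception keeps some.
- **That the folded events are ADEs, so ADE counts are too low.** Under Protocol 7.1.3 an ADE must result from the device, and Table 1 ties each effect to a device risk. Sharing a term is not enough. A site that blames the leak would probably rate the infection unrelated or unlikely, so the ADE tables change only if the adjudicated rating differs and drives them.
- **That the total loss can be calculated.** Multiplying a guessed complication rate by a guessed wound-event rate has no basis in the documents. It would also treat every co-occurring wound event as secondary and none as rescued.

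**Conclusion.** The concern holds in limited form. Item 2 can leave a Grade 1-2, non-serious wound event judged secondary without its own record, relatedness rating or adjudication. That conflicts with the stated aim of adjudicating all AEs and puts the site's view of cause ahead of the independent one. The event types affected include those Table 1 anticipates.

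The size is 0.33 percentage points per affected subject and term, assuming about 300 per group; the total is not estimable. The documents show no difference between groups in how often the rule would be applied, so they do not establish a biased comparison. The planned analysis is descriptive (SAP 3.1), so no test is affected. The sponsor should make the change because it is cheap and the affected events matter to the risk assessment, not because a large loss has been shown.

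**What to change.** Add one sentence to Protocol 7.2.2 item 2 and to the eCRF completion instructions: *Any surgical-site or wound infection, abscess, dehiscence, non-healing wound, granuloma, adhesion, or tissue or allergic reaction of a type listed in Table 1 is entered as a separate AE whatever its grade and even if judged secondary; the presumed primary cause is entered in the cause field and adjudicated by the Medical Monitor.*

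Keep the cascade rule for everything else, including infections away from the surgical site, such as pneumonia or urinary infection. Restate the rule with this exception in SAP 3.4, and note in the report that recording differs here from the closed study's convention.

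Defining the two open terms would also help, but alone it would leave minor events close in time folded.

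The cost is somewhat more AE records to adjudicate and higher total event counts. All charts are being reviewed anyway (Protocol 9.2) and the cause field exists (Protocol 9.1). Subject counts per preferred term are not inflated, because each subject still counts once per term.

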9. DATA HANDLING

9.1 Data Collection and Reporting

Data from the closed study were previously entered into an electronic data capture (EDC) system between 2013 and 2016. New electronic case report forms (eCRFs) and a new database have been created for the retrospective review and clinical monitoring functions. All required data for this study will be collected on standardized eCRFs within a 21 CFR Part 11 compliant EDC system.

A new eCRF will be completed for all previously consented subjects indicating verification of informed consent and whether any adverse events or device deficiencies were identified in the closed study Source records. Any identified AEs will be entered on a new AE eCRF. Any identified device deficiencies will be entered on a new Device Deficiency eCRF. The data to be collected are summarized below.

- For all subjects:
 - Verification of documentation of informed consent from closed study in the Source
 - Verification of signed and dated IRB-approved informed consent document
 - Verification of randomization and randomization assignment
 - Documentation of actual irrigation product used during closed study
 - Documentation of the subject's medical diagnosis requiring open abdominal laparotomy as defined in the closed study eligibility criteria
 - Documentation of the reason for open abdominal laparotomy (e.g., trauma or acute surgical abdomen)
 - Description of the nature of trauma or acute surgical abdomen and what specific surgical procedures were performed
 - Verification of whether the subject experienced any adverse events in the closed study based on review of Source records
 - Verification of whether any device deficiencies were documented in the closed study Source records
 - Copy of redacted Source operative notes to provide relevant information for adjudication of any adverse events
- For subjects who have an adverse event identified in the closed study Source records:
 - Dates of event report and when site became aware of event
 - Demographics (e.g., age, gender, race, weight, height)
 - Allergy, medical and surgical history
 - Concomitant medications taken
 - Adverse event term, type, description, onset date and timeline relative to device use, resolution date, outcome, severity and relationship to device
 - For serious events, criteria meeting SAE/SADE definition, dates of hospital admission and discharge, and/or date and cause of death, as applicable

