9.2 Monitoring Procedures

Clinical site monitoring is conducted to ensure that the reported study safety data are accurate, complete, and verifiable. A Clinical Monitoring Plan will be developed by the CRO that details the retrospective chart review of existing safety data in the clinical study, IRR-CT-901-2013-01.

Informed consent forms for all subjects who were previously consented in the clinical study, Protocol IRR-CT-901-2013-01, will be checked for proper recordkeeping and signatures. All subjects' source medical records will be reviewed for any potential adverse events or device deficiencies. All identified AEs and device deficiencies in the Source medical records will undergo CRF review with 100% source data verification. Completed eCRFs will be verified by the monitor at the study site during the monitoring visit(s). The clinical monitors will be unblinded as to the study randomization assignment.

The study may also be subject to a quality assurance audit by the Sponsor and/or an inspection by regulatory authorities. It is important that the Investigator and relevant study personnel are available during on-site monitoring visits or audits and that sufficient time is devoted to the process.

Separately, a Medical Monitoring Plan will be developed for this clinical study and will describe the process for reviewing and adjudicating all AEs. The independent Medical Monitor will be unblinded to the study randomization assignment.

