3.4 Adverse Events Analysis

AE rates will be summarized on ITT population by type of AE, occurrence rate, severity and device-relatedness, as defined below. The summary tables will document the event descriptions, the total number of events, and the number and the percentage of subjects affected in each device group to inform the Sponsor's product risk assessment.

All AEs will be coded using MedDRA. AE summaries will be presented by device group using the MedDRA level hierarchy (system organ class, high-level group term, high-level term, and preferred term) as follows:

- Overall (i.e., regardless of severity or relationship to treatment)
- By severity grade
- By relationship to study product according to the mapping scheme below:
 - Potentially related: will include all AEs with a relationship rating of "definitely", "probably" or "possibly".
 - Unlikely/not related: will include all AEs with a relationship rating of "unlikely" or "unrelated".

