3.8 Key Data Items

Study Analysis Population Definition:

- Intended-To-Treat (ITT) population: All subjects who consented into the study and were randomized to use either irrigation product (Irrisept or SoC).

Important Derived Variables:

- Age = (Screening Date – Date of Birth +1)/365.25.
- Concomitant Medication and Treatments: The medications and treatments started after enrolled to the study (date of Informed Consent).
- Treatment emergent AE or ADE (TEAE/TEADE): Any AE (ADE) started on or after the day of using study device.

Formulas of Metric Conversion:

- 1 inch = 2.54 cm
- 1 lb = 0.4536 kg
- $^{\circ}\text{C} = ({}^{\circ}\text{F} - 32) \times 5/9$

AE Severity

GRADE	DESCRIPTION
0	No AE (or within normal limits)
1	Mild; asymptomatic or mild symptoms; clinical or diagnostic observations only; intervention not indicated
2	Moderate; minimal, local, or noninvasive intervention indicated; limiting age-appropriate instrumental activities of daily living (ADL)
3	Severe or medically significant but not immediately life-threatening; hospitalization or prolongation of hospitalization indicated; disabling; limiting self-care ADL
4	Life-threatening consequences; urgent intervention indicated
5	Death related to AE

AE Relationship to Study Device

By relationship to study product according to the mapping scheme below:

- Potentially related: including the ratings of "definitely", "probably" or "possibly"
- Unlikely related: including the ratings of "unlikely" or "unrelated"

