4. OUTPUT PLANNED FOR THE STUDY REPORT

4.1 Tables to be Included in Study Report

4.1.1 *Summary of subject information*

1. Table [TDS01] Subject Disposition – ITT population
2. Table [TSC01] Summary of Surgical Procedure by Device Group – ITT Population
3. Table [TDM01] Summary of Demographics – ITT Population
4. Table [TDA01] Summary of Study Device Deficiencies – ITT Population

4.1.2 *Summary of AE*

5. Table [TAE01] Number (%) of Subjects with Adverse Events by MedDRA System Organ Class, High Level Group Term, High Level Term and Preferred Term – ITT Population
6. Table [TAE02] Number (%) of Subjects with Serious Adverse Events by MedDRA System Organ Class, High Level Group Term, High Level Term and Preferred Term – ITT Population
7. Table [TAE03a] Number (%) of Subjects with Adverse Events Grade 2 or Less by MedDRA System Organ Class, High Level Group Term, High Level Term and Preferred Term – ITT Population
8. Table [TAE03b] Number (%) of Subjects with Adverse Events Grade 3 or Higher by MedDRA System Organ Class, High Level Group Term, High Level Term and Preferred Term – ITT Population
9. Table [TAE04] Number (%) of Subjects with Adverse Events Potentially Related to Study Device by MedDRA System Organ Class, High Level Group Term, High Level Term and Preferred Term – ITT Population
10. Table [TAE05] Number (%) of Subjects with Adverse Events by Preferred Term and Overall Frequency – ITT Population
11. Table [TAE06] Number (%) of Subjects with Serious Adverse Events by SAE Criteria – ITT Population
12. Table [TAE07] Number (%) of Subjects with Adverse Events by Onset Time and Outcome – ITT Population
13. Table [TAE08] Number (%) of Subjects with Adverse Events by Severity and Relationship to Study Device – ITT Population
14. Table [TAE09] Number (%) of Subjects with Adverse Events by Action Taken and Irrisep Device Use Information – ITT Population

4.1.3 *Summary of ADE*

15. Table [TADE01] Number (%) of Subjects with Adverse Device Effects by MedDRA System Organ Class, High Level Group Term, High Level Term and Preferred Term – ITT Population
16. Table [TADE02] Number (%) of Subjects with Serious Adverse Device Effects by MedDRA System Organ Class, High Level Group Term, High Level Term and Preferred Term – ITT Population
17. Table [TADE03] Number (%) of Subjects with Unanticipated Serious Adverse Device Effects by MedDRA System Organ Class, High Level Group Term, High Level Term and Preferred Term – ITT Population

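### Preexisting conditions go on the AE form and the SAP's treatment-emergent definition is applied to no output, so pre-irrigation conditions can dilute the between-group AE summaries

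*Protocol*

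**What the plan says.** Protocol 7.2.2 item 5, one of the AE reporting rules, treats a condition as preexisting if it was there at the closed study's screening visit, and then states: "Preexisting medical conditions should be recorded on the AE CRF". Worsening is not mentioned. Protocol 9.1 makes that form the place where AEs are entered: "Any identified AEs will be entered on a new AE eCRF".

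SAP 3.8 lists TEAE/TEADE among its derived variables, defined as "Any AE (ADE) started on or after the day of using study device". The term appears nowhere else. SAP 3.4 summarizes AEs in the ITT population by MedDRA level, first "Overall (i.e., regardless of severity or relationship to treatment"), then by severity grade and by relationship, with no onset restriction. The titles in SAP 4.1 and 4.2 follow suit, for example "Table [TAE01] Number (%) of Subjects with Adverse Events by MedDRA System Organ Class". One title uses timing: "Table [TAE07] Number (%) of Subjects with Adverse Events by Onset Time and Outcome".

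**The concern.** The key endpoint in the Protocol Summary is AEs with Irrisept compared with SoC, and SAP 3.4 says the tables inform the product risk assessment. A condition present before irrigation cannot have been caused by either product. If it is counted as an AE, it adds the same kind of noise to both columns and makes the groups look more alike than they were after exposure.

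The SAP defines the variable that would largely prevent this and then does not use it. A programmer working from SAP 3.4 and the table titles would have no instruction to leave such records out.

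**Working it through.** The plan states no AE rate, sample-size target, test or interval for this review, so there is no figure of its own to reproduce. The check is one of text, followed by an illustration.

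**Text check**

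1. Entry: Protocol 7.2.2 item 5 puts preexisting conditions on the AE form without condition.
2. Definition: the AE definitions in Protocol 7.1.1 and SAP 2.2.1 contain no timing clause that would drop them.
3. Adjudication: under Protocol 7.2.1, "Each AE will be assessed by an Independent Medical Monitor for severity, relatedness to the device, seriousness categorization per the event definitions", and for whether a device effect was anticipated. None of these ratings asks whether the entry predates irrigation.
4. Tabulation: 0 of 19 tables and 0 of 26 listings are limited to TEAEs. TAE07 splits by onset but removes nothing from the other tables.
5. Medical history: SAP 3.3 and listings LMH01 and LMH02 show it separately, but do not say that items shown there leave the AE tables.

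**Where it would show.** TAE06 to TAE08 aggregate across MedDRA terms. TAE01 to TAE03b would be affected in any subject-level total they carry; the SAP gives titles only and promises no such row. Related-AE and adverse device effect outputs are largely protected, because Protocol 7.2.3 names preexisting conditions as a cause to document under an unrelated rating. The exception is SAP 3.6, which sets a missing relationship to potentially related and a missing severity to severe.

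**Illustration (assumed rates)**

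Let q be the share of subjects with a preexisting-condition entry, equal in both groups, and p the post-irrigation any-AE risk, assumed independent of having an entry.

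Observed proportion = q + (1 − q)p

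Observed difference = (1 − q)(p1 − p2)

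With p1 = 40% (Irrisept) and p2 = 30% (SoC):

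| q | Irrisept | SoC | Difference (points) | Ratio |
|---|---|---|---|---|
| 0 | 40.0% | 30.0% | 10.0 | 1.33 |
| 10% | 0.10 + 0.90 × 0.40 = 46.0% | 0.10 + 0.90 × 0.30 = 37.0% | 9.0 | 1.24 |
| 25% | 0.25 + 0.75 × 0.40 = 55.0% | 0.25 + 0.75 × 0.30 = 47.5% | 7.5 | 1.16 |
| 50% | 0.50 + 0.50 × 0.40 = 70.0% | 0.50 + 0.50 × 0.30 = 65.0% | 5.0 | 1.08 |

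For a single term, assume 6% versus 3%. If the term does not occur at baseline, nothing changes. With q = 1% for that term, 0.01 + 0.99 × 0.06 = 6.94% and 0.01 + 0.99 × 0.03 = 3.97%, a difference of 2.97 points instead of 3.00. Wound-term differences are therefore nearly untouched.

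**Can the SAP's TEAE definition be used as it stands?** Not safely. It is anchored to the study device without naming SoC, and it works by calendar day. Screening and surgery both fall in Visit 1 (SAP 1.2), so a condition that began on the day of surgery but before irrigation would still count as emergent. Protocol 9.1 already collects onset date and timing relative to device use, which allows a finer cut.

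**The case against.** The best reply is that being recorded on the AE form is not the same as being counted as an AE. Protocol 9.1 has its own fields, for every subject, for the laparotomy diagnosis, its reason and the nature of the trauma or acute abdomen. Medical history has separate fields and listings, collected only for subjects with an identified AE, a split that would lose most of its purpose if every preexisting condition were an AE. The aim is complete identification, which favours inclusive recording. Item 5 restates the closed protocol, and a Medical Monitoring Plan is still to describe adjudication; neither is available here, and either might screen such entries.

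This makes a small q plausible. It does not close the gap, because no rule in the protocol or SAP excludes item 5 entries from the tables.

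Three stronger readings are tempting and not supported:

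- **Nearly every subject would carry a Grade 3 or serious entry for the presenting disease.** The separate diagnosis fields make this remote. Protocol 7.1.2 also ties the ISO serious criteria to a serious deterioration in health. That protection is only partial: the same section's first sentence and SAP 2.2.1 omit the condition, and the explicit exclusion covers planned hospitalization or a study-required procedure without worsening.
- **Unblinded review would bias the comparison.** Protocol 9.2 does say "The clinical monitors will be unblinded as to the study randomization assignment", but Protocol 7.2.1 makes the Investigator the one who records AEs, and nothing points to unequal entry. Entries in 30% versus 20% with a true risk of 30% in both groups would give 51.0% versus 44.0%, but the 10-point recording gap is pure assumption.
- **A statistically clear difference would be lost.** SAP 3.1 plans counts and percentages only, so there is no test or interval to lose.

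The missing-data route is also narrow, since Investigators must record severity and relationship and the Medical Monitor rates each AE.

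**Conclusion.** The point holds as a defect of specification with a known direction and an unknown size. The rules as written allow pre-irrigation conditions into the between-group AE, SAE and severity summaries. With equal recording in the two groups, the effect on an any-AE difference is dilution by (1 − q): from 10.0 to 9.0, 7.5 or 5.0 points at q = 10%, 25% or 50% under the assumed risks. Neither q nor any AE rate is in the documents, and the formula assumes that entries are independent of later events. Outputs on related events, device effects and wound terms, which bear most directly on device risk, change little. It is worth correcting because the comparison is the key endpoint and the remedy is cheap, not because harm has been shown.

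**What to change.** Make the change in the SAP.

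1. State that the between-group AE, SAE and severity tables (TAE01 to TAE03b and TAE05 to TAE08) are based on TEAEs.
2. Redefine TEAE for both groups as onset, or documented worsening, after irrigation with Irrisept or SoC began. Derive it from the onset date and timing relative to device use collected under Protocol 9.1, in place of the calendar-day study-device anchor.
3. Keep the all-AE listings, and an all-AE table if wanted, so that pre-irrigation events remain reported and the completeness objective in Protocol 3 and SAP 1.1 is met.

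The cost is SAP wording and one programmed flag. The drawback is reliance on onset timing where worsening was not recorded: the data list in Protocol 9.1 has no worsening item, so a preexisting condition that worsened could be missed from the TEAE tables, although it would stay in the listings.

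Amending item 5 or adding a worsening item to the eCRF is optional. An amendment needs Investigator compliance statements (Protocol 9.5) and possibly IRB re-approval (Protocol 10), and a new item means changing a database that already exists.
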